The inclusion of a placebo treatment is critical in helping advance our understanding of the effects (both positive and negative) of ramelteon exposure. Placebo comparison is the only way that we can understand what is likely due to ramelteon and what is not.

f. Definition of treatment failure or participant removal criteria.

All consented participants will be retained in the study. Participants with no evidence of riboflavin in the urine sample as tested by fluorescence prior to surgery (i.e. evidence of non-adherence to the first dose of study agent) will continue in the study, receiving second and third doses of study agent, and undergoing delirium outcome measures at all time points; however recruitment will continue until 80 participants with documented adherence to the first doses of study agent is attained. Primary analysis will be intent to treat with all randomized subjects included in the analysis; secondary analysis will include only patients with documented adherence all 3 doses of study medication (a per protocol analysis).

Participants who have their surgery canceled after they have been randomized and who are likely to have surgery in the future will be considered "suspended" from the study. These participants will continue in their assigned condition. A new baseline will be completed prior to their new surgery date to establish that they continue to meet inclusion criteria. The team will proceed with the protocol pre- and postoperatively as assigned during the original randomization. If the participant takes any of the study medication prior to the original surgery, a minimum of 7 days between initial study dosing and the re-initiation of the protocol is required to ensure sufficient time to wash out. If the rescheduled surgery occurs less than 7 days after original dosing, the participant will be excluded from the study.

g. Description of what happens to participants receiving therapy when study ends or if a participant's participation in the study ends prematurely.

Patients will be thanked for their help with the study and will be advised to call the PI with any questions.

5. Inclusion/Exclusion Criteria

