Choice of Sample Size; Power Considerations– Why 80 adherent participants? The power to detect a difference in the development of postoperative delirium of an the previously reported effect-size²⁴(30% placebo-treated vs. 3% ramelteon-treated) is greater than 0.90, using the current design of 40 participants in each treatment arm and assuming 30% of the placebo-treated group will develop delirium on POD 1 or 2. This design can detect an 80% reduction in delirium (30% placebo-treated vs. 6% ramelteon-treated) with a power of 0.84. A conservative estimate for power for the continuous outcome (DSRS-98R) measuring delirium severity can be derived by conceptualizing the proposed longitudinal analysis as an independent samples t-test. With alpha of 0.05 and a sample size of 80, and with means in the ramelteon and placebo groups of 5.75 and 11.34, respectively (as reported in Hatta, et al), and SDs of 4.16 and 10.96, we would have 84% power to detect that difference. Power for the planned analysis, which includes 3 post-surgery measurements per participant, and controls for baseline measurement and additional covariates would likely be greater.

Data Analysis-Specific Aim 1:

Analysis 1: Odds of postoperative delirium upon immediate recovery will be modeled via logistic regression with treatment assignment as the covariate of interest, and controlling for baseline MMSE, surgical duration and sleep disorders in all randomized participants in a strict intent to treat model and also in a second analysis among the 80 first-dose adherent participants.⁹¹ Odds of delirium on POD's 1 and 2 will be modeled via a Markov logistic regression model⁹² as a function of treatment assignment, baseline MMSE, and mental status on

the previous day, where two transitions are possible: from normal mental status to delirium and/or coma (abnormal mental states) and the reverse. Correlation of mental status on consecutive days for the same individual will be modeled using generalized estimating equations (GEE).⁹² We will fit models with interactions between treatment group and variables hypothesized to predict treatment response, including baseline MMSE and sleep to determine if treatment response varies as a function of baseline predictors.

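### Section 4.f excludes randomised, already-dosed participants whose surgery is rescheduled within 7 days of dosing, which conflicts with its own intent-to-treat rule

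*Combined protocol and SAP*

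**What the plan says.** All of the conflicting text is in the combined protocol and SAP, and most of it is in Section 4.f (Definition of treatment failure or participant removal criteria).

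- Retention: "All consented participants will be retained in the study".
- Primary analysis set: "Primary analysis will be intent to treat with all randomized subjects included in the analysis". Section 7.c, Analysis 1 for Specific Aim 1, repeats this with "in all randomized participants in a strict intent to treat model" and adds a second analysis in the first-dose-adherent participants.
- Cancelled surgery: the next paragraph of 4.f concerns "Participants who have their surgery canceled after they have been randomized and who are likely to have surgery in the future". They are suspended, keep their assignment, and have a new baseline before the new date to confirm that they still qualify.
- Already dosed: "If the participant takes any of the study medication prior to the original surgery, a minimum of 7 days between initial study dosing" and restarting the protocol is required. The paragraph ends: "If the rescheduled surgery occurs less than 7 days after original dosing, the participant will be excluded from the study".

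No sentence exempts this last group from the retention or intent-to-treat rule. None says whether they stay in the analysis, how a missing delirium outcome would be handled, or whether their adverse events stay in the Aim 2 comparison.

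**The concern.** The removal rule applies only to people who have been randomised and have taken study drug. If they leave the study, the primary analysis no longer covers everyone randomised, and Section 7.c's description of it as strict is not met. Two analysts could each follow the protocol and report different denominators.

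The loss is avoidable. The rule applies only when the new surgery takes place, so PACU, POD 1 and POD 2 assessments around it are possible, with the telephone route in Sections 4.a and 4.b available after early discharge.

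There is also a safety aspect. Section 4.f does not restrict the reasons for cancellation, so one could be an event after the first dose. The assessment table in Section 7 schedules adverse-event collection at PACU, POD 1 and POD 2 only. A dosed participant who is excluded before surgery reaches none of these time points.

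**Working it through.** **Step 1. The passages side by side.** The point rests on wording and disputes no stated figure.

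| Group in 4.f | Randomised? | Took first dose? | Stated handling |
|---|---|---|---|
| No riboflavin in urine | yes | no evidence of it | stays in study, remaining doses, all delirium assessments |
| Cancelled, new surgery at least 7 days after dosing | yes | yes | protocol restarted after a new baseline, assignment kept |
| Cancelled, new surgery less than 7 days after dosing | yes | yes | excluded from the study |

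Where 4.f wants someone off plan but still followed, as in the first row, it says so. The third row has the opposite wording. Section 4.g, on early end of participation, provides only thanks and an invitation to call with questions; it mentions no further outcome collection. So a group known to have been exposed is treated less inclusively than a group with no evidence of exposure.

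**Step 2. The plan's own power figure.** Inputs from Section 7.c: 40 per arm, 30% vs 6%, alpha 0.05 (two-sided assumed), stated power 0.84. Arcsine method:

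- h = 2·arcsin(√0.30) − 2·arcsin(√0.06) = 0.664
- power = Φ(h·√(n/2) − 1.96) = Φ(0.664·√20 − 1.96) = Φ(2.971 − 1.96) = 0.844

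This reproduces the stated 0.84.

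**Step 3. Effect on power.** The documents do not say how many participants would meet the rule. As an assumed range, take 0 to 4 lost per arm without replacement:

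| Lost per arm | n per arm | Power, 30% vs 6% |
|---|---|---|
| 0 | 40 | 0.844 |
| 1 | 39 | 0.835 |
| 2 | 38 | 0.825 |
| 4 | 36 | 0.805 |

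The real loss is probably smaller, because "recruitment will continue until 80 participants with documented adherence to the first doses of study agent is attained". The problem is therefore the definition of the analysis set, not sample size.

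**Step 4. Could one participant change the result?** At 30% vs 6% the expected events are 0.30 × 40 = 12 and 0.06 × 40 = 2.4. At 30% vs 3%, the other scenario in Section 7.c, they are 12 and 1.2. Add one retained ramelteon participant with delirium to tables near these values, and to two tables with a smaller effect (two-sided Fisher exact; Pearson without continuity correction):

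| Without | With one added | Fisher p | Pearson p |
|---|---|---|---|
| 12/40 vs 1/40 | 12/40 vs 2/41 | 0.0015 → 0.0032 | 0.0009 → 0.0028 |
| 12/40 vs 2/40 | 12/40 vs 3/41 | 0.0064 → 0.0105 | 0.0033 → 0.0086 |
| 12/40 vs 3/40 | 12/40 vs 4/41 | 0.0198 → 0.0274 | 0.0099 → 0.0221 |
| 12/40 vs 4/40 | 12/40 vs 5/41 | 0.0482 → 0.0600 | 0.0253 → 0.0491 |

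Only the last row crosses 0.05, and only under Fisher. It corresponds to 30% vs 10%, which is not a scenario in the protocol. The planned tests are adjusted logistic regression and a Markov model with GEE, so the table is an illustration only.

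**The case against.** **The exclusion may be from the study procedures, not from the analysis.** The section is about removal criteria, and a specific exception may follow a general rule. On this reading the protocol stops but the participant still counts as randomised. The text neither says this nor rules it out. It would leave these people in the intent-to-treat set with no delirium outcome and no rule for handling that, so the sentences would still need reconciling. The contrast with the riboflavin-negative group in the same section also counts against it.

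**The scope for bias is limited.** This stands. The trigger comes before the new surgery and before any delirium outcome, and Section 4.c blinds study staff, clinical staff and patients. Exclusion cannot depend on known allocation or on the outcome. Masking does not prevent imbalance if an effect of the drug itself led to the cancellation, but the documents give no evidence that this would happen.

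**The safety data are not necessarily lost.** This stands in part. Section 7.a also takes adverse events from the medical record, Section 8.c sends them all to the IRB and DSMB, and nothing voids an event already recorded. Participants rescheduled later than the 7-day limit may restart and contribute. A reader might infer that the safety comparison would lose exactly those harmed by the first dose. The documents do not support that; they show only that inclusion of such events in Aim 2 is not assured.

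**One participant could overturn the trial.** A reader might infer this from the small number of expected events. At the effects the protocol plans for it is not so; it needs a result already at the 0.05 boundary.

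**Conclusion.** The concern holds in a limited form. Section 4.f states a rule that, followed as written, removes randomised and exposed participants and so conflicts with the intent-to-treat set defined in 4.f and 7.c. It discards delirium outcomes that could be collected, and it may leave adverse events after the first dose out of the Aim 2 comparison.

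This is a minor point that is worth correcting. Probably few participants would be affected, although this is a judgement because the documents give neither counts nor reasons for cancellation. Under the assumed range of 0 to 4 lost per arm, power for 30% vs 6% would fall from 0.844 to no lower than 0.805, before allowing for continued recruitment. The documents do not support a claim of demonstrated bias or of a conclusion that depends on one participant.

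A related gap is in the same paragraph. The repeat baseline after a cancelled surgery checks eligibility again, but the plan does not say how a participant who fails it is analysed. Correcting only the 7-day sentence would leave that second possible exclusion after randomisation.

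**What to change.** Reconcile the sentences in Section 4.f without changing the washout or dosing rules:

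1. Replace the exclusion from the study with wording that keeps these participants in follow-up: delirium assessments in the PACU and on POD 1 and POD 2, and adverse events, around the surgery that takes place.
2. State that they are analysed as randomised in the intent-to-treat and safety sets, and omitted only from the per-protocol and first-dose-adherent sets.
3. State that adverse events after the first dose count in Aim 2 even when they occur before the rescheduled surgery.
4. Apply the same analysis rule to anyone who fails the repeat baseline after a cancelled surgery, and say how a missing delirium outcome is handled.

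Whether any study drug is given around the rescheduled surgery is for the sponsor to settle; this point takes no view on it.

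The cost is a few sentences in 4.f, the usual assessments for probably a handful of people, and slight dilution of the treatment contrast by incompletely treated participants. The intent-to-treat rule already accepts such dilution for the riboflavin-negative group.

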We propose a proof-of-concept (phase 2) double-blind randomized placebo-controlled trial to evaluate the efficacy and short-term safety of ramelteon for the prevention of postoperative delirium in a high-risk group of patients, 65 years and older, with MMSE²⁵ scores ≥ 15 , planned orthopedic surgery. Our prior work demonstrates the feasibility of conducting a prevention trial in this population, using state-of-the-art delirium detection and diagnosis methodology.^{5,25} Should this preliminary trial, show evidence of efficacy and adequate safety, then a phase 3 trial will be proposed.

Our group has demonstrated that an early predictor of subsequent delirium is the presence of delirium immediately upon recovery from general anesthesia in the post anesthesia care unit (PACU).^{5,26,27} The proposed trial will incorporate assessment of PACU delirium as a means of early delirium detection in helping to determine the efficacy of the ramelteon intervention.

2. **Objectives (include all primary and secondary objectives)** The proposed trial will involve administering 8 mg ramelteon orally (1 dose preoperatively and 2 doses postoperatively) or placebo in 80 older-aged patients to test the following:

Specific Aim 1 (primary outcome): To compare delirium incidence and severity between ramelteon and placebo using the DSM 5 criteria by expert panel consensus.

Hypothesis 1: Compared to placebo, ramelteon will be associated with a) a lower incidence and severity of postoperative delirium immediately upon recovery from anesthesia in the PACU, and b) with a lower incidence and severity of delirium on postoperative day (POD) 1 and POD 2.

Specific Aim 2 (safety outcome): To compare adverse events (AEs) and serious adverse events (SAEs) between ramelteon and placebo.

Hypothesis 2: Ramelteon will have an adequate safety profile in this postoperative cohort, sufficient to support conducting a larger prevention trial. Specifically, compared to placebo, ramelteon will not be associated with increased incidence of postoperative delirium or with increased adverse side effects including fatigue, headache and next day somnolence during the treatment episode.

3. Background (briefly describe pre-clinical and clinical data, current experience with procedures, drug or device, and any other relevant information to justify the research)

a. Significance:

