Choice of agent and dose: Ramelteon is fast in onset. In a study of its safety and efficacy in older adults with chronic primary insomnia, using a two night crossover double-blind randomized controlled design, 8 mg of ramelteon demonstrated statistically significant decreases in sleep latency, increased sleep efficiency, and total sleep time compared to placebo as measured by polysomnography.⁷⁸ A 'first night' model of transient insomnia in 289 patients, naïve to a sleep laboratory environment and without any prior sleep difficulties, demonstrated similar findings with exposure to one dose.⁷¹ Increased side effects, including fatigue, headache, and next-day somnolence, were experienced with 16 mg vs 8 mg, with no additional sleep architecture benefit.⁶⁰ Ramelteon (8 mg dose) is rapidly absorbed with peak serum concentrations at 1 hour and results in 20 -30 times the equivalent of nocturnal plasma melatonin levels. Such superphysiologic dosing may confer additional melatonergic neuroprotective benefits. Easily absorbed and highly protein bound, ramelteon is subject to extensive first pass metabolism, and rapidly eliminated ($t_{1/2}$ =1-2.6 hours). However the M II metabolite is highly biologically active, binding to both melatonin and serotonin-2B receptors. Elderly individuals metabolize ramelteon less rapidly than younger subjects, resulting in a doubling of exposure, given the same dose.^{60,79} **Use of 8 mg of ramelteon in this protocol should confer both sleep promoting and circadian rhythm maintenance, and is a sufficient dose to provide superphysiologic melatonin receptor stimulation potentially consistent with antioxidant effects at a dose with relatively few side effects.**

b. Justification and safety information if FDA approved drugs will be administered for non-FDA approved indications or if doses or routes of administration or participant populations are changed.

An FDA waiver of need for IND was received on January 5th 2015 (see attached letter rejecting application for IND). One of the reasons given by the FDA was that the “investigation does not involve a change in route of administration, dosage or population, or other factor that significantly increases the risks (or decreases the acceptability of risks) associated with the use of the drug product.”

- c. Justification and safety information if non-FDA approved drugs without an IND will be administered. – Not applicable.

7. Study Statistics

- a. Primary outcome variables.

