Outcome Measure Specific Aim I – State-of-the-Art Delirium Assessment and Diagnosis: Well-trained research staff will conduct delirium assessments at baseline, to exclude cases of prevalent delirium, and at three later time points (see Figure and Table). This assessment includes: (1) face to face standardized interview of the patient regarding experiences, (2) standardized cognitive testing including the MMSE⁷⁵ and the abbreviated Digit Span,⁸⁰ (3) history from family/friends familiar with the patient’s cognitive baseline, (4) interview of nursing and other medical staff caring for the patient, and (5) review of medical records for evidence of behavioral disturbances and symptoms in previous 24 hours. Information on sleep disturbance is sought from all sources and is a symptom of delirium. Assessors will rate the CAM⁸¹ and the Delirium Rating Scale-Revised ’98 (DRS-R98)⁶² for the prior 24 hours and describe the patient’s behavior and mental state in a written narrative. If a patient is intubated the CAM-ICU⁸² will be administered to determine delirium status. Patients who are comatose will be documented as such. (Preliminary data suggests that this is a rare occurrence <1%) Final adjudication of delirium diagnosis is derived after all data is presented to a panel of expert delirium diagnosticians ([name]).

The primary diagnosis of delirium is based upon meeting all DSM-5 criteria (see appendix), and is determined by consensus of the expert panel - a method currently employed by this group of co-investigators in the STRIDE study.

A second outcome measure will be analyzed using the continuous variable of delirium severity derived from the DRS-98R severity measure.

Outcome Measure Specific Aim II- Adverse Events: All adverse events (AE and SAE) will be collected from the medical record and daily patient assessment using a customized instrument (“Health Questionnaire”) which will systematically probe for known side effects (fatigue, headache and next day somnolence) (see Protection of Human Subjects). Assessment of Outcome and Covariates:

Table: Timing and Content of Patient Assessments

Assessments	Administration	Collection Instrument and Source
Cognition	Preoperative, PACU POD 1 and 2	Mini Mental State Exam Abbreviated Digit Span: Forwards and Backwards
Delirium	Preoperative, PACU, POD 1 and 2	CAM (full) ⁸³ after patient exam + proxy/medical record review or CAM-ICU if intubated; DRS-98R (severity measure)

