Risks associated with the Study Treatment: Ramelteon has FDA approval for use in elderly patients with insomnia. However this agent has never been used peri-operatively in older patients undergoing general or regional anesthesia and we cannot be certain that it will be safe in this setting. Therefore the study aims to test safety of this agent compared to placebo; we will systematically collect daily information on adverse (AE) and serious adverse events (SAE) that occur in each arm of the study. The main potential risk is one of increased incidence of delirium due to the treatment intervention. Other risks associated with the use of ramelteon reported in product labeling include: 1) angioedema and anaphylactic reactions – this risk is extremely rare; 2) worsening of insomnia, or the emergence of new cognitive or behavioral abnormalities that may be the result of an unrecognized underlying psychiatric or physical disorder, such as worsening of depression (including suicidal ideation and completed suicides), hallucinations, bizarre behavior, agitation and mania; 4) amnesia, anxiety and other neuro-psychiatric symptoms may also occur unpredictably, including complex behaviors such as "sleep-driving" (i.e., driving while not fully awake after ingestion of a hypnotic) and other complex behaviors (e.g., preparing and eating food, making phone calls, or having sex) with amnesia for the event; 5) decreased testosterone levels and increased prolactin levels have been reported with long-term use; 7) the use is contraindicated in severe hepatic failure as evidenced by cirrhosis, ascites, portal hypertension and prolonged bleeding times; 8) also contraindicated with the concomitant use of fluvoxamine; and finally 9) caution is to be used when prescribing with other CYP enzyme active agents such as rifampin, fluconazole, and ketoconazole. Other less serious side effects that have been reported in clinical trials include somnolence, fatigue, dizziness, nausea and worsened insomnia.

The following is taken from the ramelteon package insert:

ADVERSE REACTIONS

The following serious adverse reactions are discussed in greater detail in other sections: Severe anaphylactic and anaphylactoid reactions [see Warnings and Precautions (5.1)] Abnormal thinking, behavior changes, and complex behaviors [see Warnings and Precautions (5.3)] CNS effects [see Warnings and Precautions (5.4)]

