6.1 Clinical Trials Experience

Adverse Reactions Resulting in Discontinuation of Treatment

The data described in this section reflect exposure to ROZEREM in 5373 subjects, including 722 exposed for 6 months or longer, and 448 subjects for one year.

Six percent of the 5373 individual subjects exposed to ROZEREM in clinical studies discontinued treatment owing to an adverse event, compared with 2% of the 2279 subjects receiving placebo. The most frequent adverse events leading to discontinuation in subjects receiving ROZEREM were somnolence, dizziness, nausea, fatigue, headache, and insomnia; all of which occurred in 1% of the patients or less.

ROZEREM Most Commonly Observed Adverse Events

Table 1 displays the incidence of adverse events reported by the 2861 patients with chronic insomnia who participated in placebo-controlled trials of ROZEREM.

Because clinical trials are conducted under widely varying conditions, adverse reaction rates observed in the clinical trials of a drug cannot be directly compared to rates in clinical trials of other drugs, and may not reflect the rates observed in practice. The adverse reaction information from clinical trials does, however, provide a basis for identifying the adverse events that appear to be related to drug use and for approximating rates.

Table 1. Incidence (% of subjects) of Treatment-Emergent Adverse Events

Term	Placebo (n= 1456)	Ramelteon 8 mg (n=1405)
Somnolence	2 %	3%
Fatigue	2%	3%
Dizziness	3%	4%
Nausea	2%	3%
Insomnia exacerbated	2%	3%

b. Steps taken to minimize the risks.

We will adhere to the exclusion criteria listed above which will help avoid the recruitment of patients most at risk of side effects and adverse consequences. Patients will be interviewed each day for any side effects and the medical records will be reviewed and the data collected for Aim 2 of the study. A DSMB will review the data as described above and the study will be halted if there is evidence of harm significantly associated with the intervention. We will also inform participants of the risks – particularly when taking the first dose at home. Specifically we will advise them to call 911 or come to an emergency room if, after taking the study drug, they develop any swelling, rash, difficulty or noisy breathing.

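### The Health Questionnaire's named probes leave out dizziness and nausea, which the protocol's own risk list and 8 mg versus placebo table name, and no rule carries worsened sleep into the adverse event counts

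*Combined protocol and SAP*

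**What the plan says.** All references are to the combined protocol and SAP.

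- **General collection.** Section 7.a, Outcome Measure Specific Aim II: "All adverse events (AE and SAE) will be collected from the medical record and daily patient assessment". Section 8.b adds a daily patient interview about side effects of any kind, with record review.
- **Named probes.** The same paragraph of section 7.a describes a Health Questionnaire "which will systematically probe for known side effects (fatigue, headache and next day somnolence"). The bracket closes there, with no wording to mark the three as examples. The assessment table schedules adverse event collection in the PACU and on POD 1 and 2.
- **Safety hypothesis.** Hypothesis 2 in section 2 names the same three, but openly: "increased adverse side effects including fatigue, headache and next day somnolence during the treatment episode".
- **Dose rationale.** Section 6.a: "Increased side effects, including fatigue, headache, and next-day somnolence, were experienced with 16 mg vs 8 mg".
- **Risk list.** Section 8.a: "Other less serious side effects that have been reported in clinical trials include somnolence, fatigue, dizziness, nausea and worsened insomnia".
- **Label data.** Section 8.a reproduces from the package insert "Table 1. Incidence (% of subjects) of Treatment-Emergent Adverse Events", comparing 8 mg with placebo on the same five terms.
- **Sleep.** Section 7.b collects the Richards Campbell questionnaire on POD 1 and 2. Section 7.a has sleep disturbance sought from every source in the delirium assessments.
- **Use of the counts.** Section 7.c models total adverse event counts by arm, and examines counts of each type to work out the power that future trials would need to study them.

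**The concern.** The instrument is presented as probing the known side effects, yet two effects that the same protocol lists as known at the trial dose are missing from the named probes. Events that are asked about by name are recorded more consistently than events that depend on a general question or on what a nurse happened to chart. Two features of this trial make that matter more. Participants may have an MMSE as low as 15, and the outcome under study is itself a disturbance of cognition, so an open question may be answered unevenly. Participants discharged before POD 2 are followed by telephone (section 4.b), with no inpatient chart for the days after discharge.

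Aim 2 is meant to show whether the drug's safety supports a larger trial, in a setting where section 8.a says it has not been used before. Rates by event type are one of the products the pilot hands on. If dizziness and nausea are under-recorded, the rates handed on will be too low.

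**Working it through.** The plan states no figure on this point, so there is none to reproduce. The check sets the lists side by side and then sizes the consequence.

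**Step 1: the lists compared**

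| Effect | Named probe (7.a) | Named as higher on 16 mg than 8 mg (6.a) | Risk list (8.a) | Table 1, placebo / 8 mg | Other named instrument |
|---|---|---|---|---|---|
| Somnolence | yes | yes | yes | 2% / 3% | not needed |
| Fatigue | yes | yes | yes | 2% / 3% | not needed |
| Headache | yes | yes | no | no row | not needed |
| Dizziness | no | no | yes | 3% / 4% | none |
| Nausea | no | no | yes | 2% / 3% | none |
| Worsened insomnia | no | no | yes | 2% / 3% | Richards Campbell (POD 1, 2); delirium assessments |

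Table 1 gives no ground for prompting somnolence and fatigue but not nausea (the same figures) or dizziness (the same one-point difference). Dizziness and nausea have no named prompt anywhere in the documents. Worsened insomnia has a route to being observed, but none to being counted as an adverse event.

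**Step 2: how firm the Table 1 differences are**

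Inputs: 1,456 on placebo, 1,405 on 8 mg, percentages as printed. Counts are back-calculated from rounded percentages, which is an assumption.

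- Dizziness: 0.03 × 1,456 ≈ 44 and 0.04 × 1,405 ≈ 56. SE = √(0.03×0.97/1,456 + 0.04×0.96/1,405) ≈ 0.0069. Difference 1.0 point, 95% CI about −0.3 to +2.3; Fisher p about 0.19.
- Nausea (the same for insomnia): 0.02 × 1,456 ≈ 29 and 0.03 × 1,405 ≈ 42. SE = √(0.02×0.98/1,456 + 0.03×0.97/1,405) ≈ 0.0058. Difference 1.0 point, 95% CI about −0.1 to +2.1; Fisher p about 0.09.
- Rounding alone allows an observed difference anywhere from about 0 to 2 points.

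The table therefore shows recognised effects, not established excesses.

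**Step 3: what this trial could see**

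At 40 per arm and Table 1 rates, expected counts are 40 × 0.02 = 0.8 against 40 × 0.03 = 1.2 for nausea, and 40 × 0.03 = 1.2 against 40 × 0.04 = 1.6 for dizziness. Power to detect an excess (normal approximation, two-sided 0.05 assumed) is Φ[(d − 1.96·SE₀)/SE₁], with SE₀ pooled and SE₁ unpooled:

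- Nausea: (0.01 − 1.96×0.0349)/0.0349 ≈ −1.67, power about 4.7%.
- Dizziness: (0.01 − 1.96×0.0411)/0.0411 ≈ −1.72, power about 4.3%.

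Prompting would not make such differences detectable here.

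**Step 4: what under-recording does**

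Suppose a fraction s of true events is recorded, equal in both arms, with no false positives. The recorded rates are s·p₁ and s·p₀: the ratio is unchanged and the difference shrinks to s·(p₁ − p₀). For dizziness, with illustrative values of s:

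| s | 8 mg | Placebo | Difference | Ratio |
|---|---|---|---|---|
| 1.0 | 4.0% | 3.0% | 1.0 | 1.33 |
| 0.8 | 3.2% | 2.4% | 0.8 | 1.33 |
| 0.5 | 2.0% | 1.5% | 0.5 | 1.33 |

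The documents give no value for s. What suffers is the rate itself and the absolute difference.

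**The case against.** Much of the case on the other side stands. The plan collects all adverse events, interviews every patient daily and reviews the record, so lacking a named prompt is not the same as being left to chance. If dizziness or nausea is charted, for whatever suspected cause, record review should find it. Nothing in the plan excludes it.

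Three stronger readings are tempting, and the documents do not support them.

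- **That three of the five Table 1 effects go unelicited.** Postoperative sleep is systematically asked about, so only dizziness and nausea lack a prompt. For insomnia the gap is the missing link to adverse event reporting.
- **That the probe list was lifted from the wrong dose comparison.** The three probes match those named in section 6.a for 16 mg against 8 mg, but the protocol does not say where the list came from. The same section says that older people get about twice the exposure from a given dose, which makes effects that rise with exposure a reasonable priority. Headache also appears in section 8.a among the most frequent events leading to discontinuation.
- **That the comparison is biased toward no difference.** Collection is masked and the same in both arms. As Step 4 shows, equal under-recording leaves the ratio alone. Only the absolute scale shrinks.

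It is also fair to say that the questionnaire form is not among the documents available, so the bracket in section 7.a cannot be shown to be its full content. The low power in Step 3 limits the practical weight of the point, but does not remove it: section 7.c wants the by-type counts for planning, where the rate matters even if no test could succeed.

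**Conclusion.** The point holds as a modest one. The closed list of probes in section 7.a does not agree with the protocol's own account of known effects at 8 mg. Dizziness and nausea have no named prompt, and worsened sleep has no stated path into the adverse event data. The likely result is less consistent ascertainment, and probably understated rates, of dizziness and nausea in the Aim 2 counts and in the figures passed to later trials. The relative comparison between arms is not clearly biased. The delirium endpoint and the sample size are unaffected.

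This rests on two assumptions: that the bracket describes the form as used, and that prompted events are recorded more completely than unprompted ones. The size of the understatement cannot be derived from the documents.

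**What to change.** 1. Add fixed yes/no prompts for dizziness and nausea to the Health Questionnaire at each scheduled administration (PACU, POD 1 and POD 2, including telephone contacts). Keep the three existing prompts.
2. State how worsened sleep found through the Richards Campbell questionnaire or the delirium assessments becomes, or does not become, a recorded adverse event.
3. Bring the lists in section 2 (Hypothesis 2) and section 7.a into line with the risk list and Table 1 in section 8.a.
4. Report dizziness and nausea by type and arm as well as within the total.

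If the form already contains these prompts, only the section 7.a wording needs correcting, along with items 2 and 4.

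The cost is two questions on an existing form and a wording amendment. The drawback is a probable rise in background counts in both arms. That may add noise to the total adverse event comparison, which is the reason for item 4.
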